5.2 Agent Administration

CONFIDENTIAL

This document is confidential. Do not disclose or use except as authorized.

5.2.1 Proton beam therapy will be planned based on patient supine CT simulation with custom immobilization per standard practice in the Department of Radiation Oncology, Massachusetts General Hospital.

5.2.2 Full contours will be obtained for all abdominal organs at risk including: stomach, duodenum, bowel (small bowel will be contoured separately if patient requires boost with teletherapy), rectum, liver, kidneys, spinal cord, thoraco-lumbar spine T12-L5, pelvic bone girdle, and proximal femurs from the femoral heads to below the lesser trochanters.

5.2.3 Comparative treatments plans for IMRT and 3DCRT will be generated for each participant from the same CT-simulation data set for comparison purposes and for actual treatment of participants in the event of the proton beam being unavailable for any reason longer than 2 working days.

5.2.4 Standard immobilization-stabilization procedures and treatment verification procedures will be employed as customarily performed for patients at the FHBPTC.

5.2.5 For participants undergoing proton beam therapy to the pelvis, the superior extent of the target volume will be at the interspace of the fifth lumbar vertebra and the first sacral segment (L5-S1).

5.2.6 For participants undergoing proton beam therapy to an extended volume (pelvic and para-aortic nodal basins) the superior border will be at the interspace of the twelfth thoracic and the first lumbar vertebrae (T12-L1).

5.2.7 For participants treated for cervical cancer the inferior extent of the target volume will encompass the proximal 2 cm of the vagina.

5.2.8 For participants treated for uterine cancer, the inferior extent of the target volume will encompass the full extent of the vagina from the apex to the introitus defined as the external urethral meatus.

5.2.9 All proton beam teletherapy treatments will be administered at a daily dose of 1.8 Gy (RBE). The RBE for proton radiation is set at 1.1. The dose unit Gy (RBE) is defined as the proton dose in Gy x RBE 1.1.

5.2.10 All proton beam teletherapy treatments will be administered no more than 5 treatment days per week.

5.2.11 Total absorbed teletherapy dose will be 45 Gy (RBE) in 25 daily fractions of 1.8 Gy (RBE) over 6 weeks for all participants except as noted in 5.2.12.

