5.2.14 Target coverage requirements

- $V_{90} \geq 90\% \text{ (40.5 Gy (RBE))}$
- $D_{97}(43.65 \text{ Gy (RBE)}) \geq 97\%$
- $D_{99}(44.55 \text{ Gy (RBE)}) \geq 90\%$
- $D_{110}(49.5 \text{ Gy (RBE)}) \leq 10\%$
- $D_{115}(51.75 \text{ Gy (RBE)}) \leq 1\%$
- Dose maximum should occur within the PTV

For patients not receiving reduced volume “boost” therapy:

Organs at risk (OAR) hard constraints:

- Bowel (including duodenum, large bowel): $V_{45} \leq 250 \text{ cc}$; $D_{\max} \leq 50 \text{ Gy (RBE)}$
- Rectum: $D_{\max} \leq 50 \text{ Gy (RBE)}$
- Bone Marrow: $V_{10} \leq 90\%$; $V_{20} \leq 75\%$
- Bladder: $D_{\max} \leq 50 \text{ Gy (RBE)}$
- Femoral Head: $D_{\max} \leq 50 \text{ Gy (RBE)}$
- Spinal cord: $D_{\max} \leq 36 \text{ Gy (RBE)}$
- Cauda: $D_{\max} \leq 50 \text{ Gy (RBE)}$
- Stomach: $D_{\max} \leq 42 \text{ Gy (RBE)}$
- Kidneys: $V_{18} \leq 30\%$ and $V_{10} \leq 50\%$ (for each kidney)

OAR soft constraints:

- Bowel: $V_{45} \leq 200 \text{ cc}$; $V_{40} \leq 30\%$; $D_{\max} \leq 45 \text{ Gy (RBE)}$

CONFIDENTIAL

This document is confidential. Do not disclose or use except as authorized.

- Rectum: $V_{45} \leq 50\%$; $V_{30} \leq 60\%$; $D_{max} \leq 50$ Gy (RBE)
- Bone Marrow: $V_{10} \leq 80\%$; $V_{20} \leq 66\%$
- Bladder: $V_{45} \leq 50\%$; $D_{max} \leq 50$ Gy (RBE)
- Femoral Head: $V_{30} \leq 15\%$; $D_{max} \leq 50$ Gy (RBE)
- Cauda Equina: $D_{max} \leq 42$ Gy (RBE)
- Kidneys: $V_{14} \leq 30\%$ (for each kidney)

For patients receiving reduced volume supplementary “boost” radiation:

- Small Bowel: $D_{max} \leq 52$ Gy (RBE)
- Large Bowel: $D_{max} \leq 56$ Gy (RBE)
- Cauda Equina: $D_{max} \leq 56$ Gy (RBE)
- Rectum: $D_{max} \leq 56$ Gy (RBE)
- Bladder: $D_{max} \leq 56$ Gy (RBE)
- Femoral Head: $D_{max} \leq 56$ Gy (RBE)

The deviations in dose constraints described are considered planning deviations only and will not constitute protocol deviations. Treatment plans that include minor planning deviations may be delivered as part of this protocol.

5.2.15 Vaginal brachytherapy will be administered on an outpatient basis employing standard techniques with high dose rate (HDR) remote afterloading equipment.

5.2.16 Cervix cancer patients will receive 3 brachytherapy fractions of 5 Gy each (15 Gy total) administered to the proximal 2 cm of the residual vagina with dose specified at the vaginal mucosa (surface of the intra-vaginal applicator).

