13.6 Multi-center Guidelines: N/A

14. STATISTICAL CONSIDERATIONS

CONFIDENTIAL

This document is confidential. Do not disclose or use except as authorized.

The primary objective of this protocol is to determine whether the substitution of scanning pencil beam proton teletherapy for conventional photon teletherapy will administer less radiation dose to the normal tissues of organs at risk compared to conventional techniques (IMRT or 3-D conformal teletherapy). Additional endpoints are to determine whether scanning pencil beam proton teletherapy is associated with cancer control rates within the irradiated volumes comparable to those reported in existing literature and to determine the rates of acute radiation side effects and delayed radiation complications.

14.1 Study Design/Endpoints:

The primary endpoint is the comparison of dose volume histograms (DVH) from proton teletherapy and conventional photon teletherapy. Structure sets contoured for proton beam treatment will be used to plan alternative IMRT and 3DCRT plans by the same medical physics team and attending physician, and DVH will be generated for each plan. It is hypothesized that the area under the DVH curve will be at least 25% smaller in the bowel, in favor of the proton plan, for virtually all patients. With a sample size of 22 patients, we will have 91% power to accept that the proton plan is superior for 95% of patients if at least 20 of them have a proton plan with an area under the DVH curve at least 25% smaller in the bowel. The decision rule is associated with type 1 error of 15% if only 80% of patients truly have a superior proton plan for the bowel. This magnitude of radiation dose difference is expected to be clinically significant with respect to acute GI side effects, thus GI toxicities will be a major focus of the data analysis to explore the correlation between DVH and radiation effects.

14.2 Sample Size/Accrual Rate:

As of October 2016, 9 node positive uterine cancer patients and 5 node positive cervical cancer patients have been enrolled and treated with proton beam teletherapy. We project another 8 patients will be enrolled and treated by the end of 2018 for a total accrual of 22 patients. Based on the tumor distribution to date, we expect the final accrual will consist of approximately 14 uterine cancer patients and 8 cervical cancer patients. Patients who do not start protocol treatment will be replaced.

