14.3 Stratification Factors: N/A

14.4 Analysis of Secondary Endpoints:

CONFIDENTIAL

This document is confidential. Do not disclose or use except as authorized.

Secondary endpoints are QOL, progression-free survival and patterns of recurrence. QOL outcomes will be analyzed using mixed models for longitudinal data. Progression-free survival will be analyzed using standard methods for failure time data, primarily the Kaplan-Meier estimate. Progression-free survival is defined as the duration from the start of protocol treatment to the time of objective disease progression at any site or death in the absence of documented progression, while patients who have not progressed or died will be censored at the time of last follow-up. Differences between patient subgroups may be explored by the log-rank test, using exact methods as the event numbers will be modest. Patterns of recurrence will be reported descriptively.

14.5 Reporting and Exclusions;

All patients starting protocol therapy will be analyzed and reported for all study endpoints, whether or not treatment is completed.

14.5.1 Evaluation of toxicity.

All participants will be evaluable for toxicity from the time of their first treatment.

14.5.2 Evaluation of response. N/A. Patients with measurable disease are ineligible.

14.5.3 Evaluation of cancer control. At or before each scheduled follow-up surveillance visit patients will be categorized as clinically cancer-free, alive with cancer, dead from cancer, dead from complications of therapy, or dead from intercurrent illness, or cause of death unknown.

14.5.4 Pattern of cancer recurrence: In patients developing cancer recurrence, the pattern of recurrence will be recorded according to the criteria in 10.2 for local, regional and distant sites. As a patient may recur at multiple sites and at different times, the dates of recurrence will be recorded for each site. Progression-free survival will be based on the date of the earliest date of documented recurrence.

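### The primary endpoint needs only completed plans, yet patients who are planned but never start treatment are replaced and leave the primary count

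*Combined protocol and SAP*

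**What the plan says.** Section 14.1 defines a planning endpoint: "The primary endpoint is the comparison of dose volume histograms (DVH) from proton teletherapy and conventional photon teletherapy". The same section sets the size and power: "With a sample size of 22 patients, we will have 91% power to accept that the proton plan is superior for 95% of patients". Acceptance depends on a count of successes, which the plan words as follows: "if at least 20 of them have a proton plan with an area under the DVH curve at least 25% smaller in the bowel". The stated cost is a "type 1 error of 15% if only 80% of patients truly have a superior proton plan for the bowel".

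Three rules then decide who is counted:

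- Section 14.2: "Patients who do not start protocol treatment will be replaced".
- Section 14.5: "All patients starting protocol therapy will be analyzed and reported for all study endpoints, whether or not treatment is completed".
- Section 4.1 has the protocol status changed, and refers to cancelling the registration, when a registered patient does not receive protocol therapy.

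On planning, section 5.2.3 says: "Comparative treatments plans for IMRT and 3DCRT will be generated for each participant". These plans use the same CT simulation as the proton plan and also serve as backup treatment plans if the proton beam is unavailable for more than 2 working days. Section 5.2.14 lists target and organ constraints, classes departures from them as planning deviations rather than protocol deviations, and adds: "Treatment plans that include minor planning deviations may be delivered as part of this protocol".

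**The concern.** Defining the analysed group by the start of treatment suits toxicity, quality of life and progression-free survival, which have no meaning before treatment. It does not suit an endpoint that needs a CT simulation and a set of plans but no delivered dose. The proton plan must exist before the first fraction. Section 14.1 has the same physics team and attending physician produce the photon plans, so those deciding whether to proceed may already know how the plans compare.

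If a planned patient does not start, her result leaves the numerator and the denominator, and a new patient takes her place. If her plan missed the 25% bowel criterion, a failure has been exchanged for a fresh chance of success. With a margin of two failures, one such exchange can turn 19 of 22 (not accepted) into 20 of 22 (accepted). The hypothesis in 14.1 concerns virtually all patients, and conditioning on starting narrows that population after the result could be known.

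**Working it through.** **Inputs from section 14.1.** n = 22; accept if at least 20 succeed; unfavourable true rate 0.80; favourable true rate 0.95; stated power 91% and type I error 15%.

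**Input from section 14.2.** 14 patients already enrolled and treated (9 uterine, 5 cervical), with 8 more projected.

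**Assumption.** d is the share of failing-plan patients who never start and are replaced. The documents give neither d nor a count of non-starters, so I use the range 0 to 0.5.

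**Step 1: reproduce the plan's figures (exact binomial).**

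- Type I error = P(X ≥ 20 | 22, 0.80) = 0.1065 + 0.0406 + 0.0074 = 0.1545. The stated 15% is confirmed to the whole percent.
- Power = P(X ≥ 20 | 22, 0.95) = 0.2070 + 0.3746 + 0.3235 = 0.9052. The stated 91% is confirmed.

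**Step 2: replacement unrelated to plan quality.** The success rate among starters stays 0.80, so the type I error stays 0.1545. There is no bias.

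**Step 3: only failing-plan patients are lost, at a true rate of 80%.** The success rate among starters is

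p = 0.8 / [0.8 + 0.2(1 − d)].

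If all 22 places are affected, the type I error is P(X ≥ 20 | 22, p). If only the 8 remaining places are affected, it is P(X₁ + X₂ ≥ 20), with X₁ binomial(14, 0.80) and X₂ binomial(8, p).

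| d | p among starters | Type I error, all 22 affected | Type I error, only the last 8 affected |
|---|---|---|---|
| 0 | 0.800 | 0.154 | 0.154 |
| 0.10 | 0.816 | 0.203 | 0.171 |
| 0.25 | 0.842 | 0.302 | 0.199 |
| 0.50 | 0.889 | 0.551 | 0.259 |

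The expected number replaced when all 22 are affected is 22/(1 − 0.2d) − 22. This is 0.4, 1.2 and 2.4 patients for d = 0.10, 0.25 and 0.50.

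**Step 4: soften the assumption.** If 25% of failing-plan patients and 10% of succeeding-plan patients are lost across all 22 places, p = 0.72/(0.72 + 0.15) = 0.828 and the type I error is 0.243, against 0.302 in step 3.

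**Step 5: restore the lost failures to a passing result.** With 20 successes among 22 starters, adding back 1, 2 or 3 planned failures gives 20/23 = 87.0%, 20/24 = 83.3% or 20/25 = 80.0%.

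**Step 6: cut-offs if the denominator grows.**

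| Rule | Type I error at 0.80 | Power at 0.95 |
|---|---|---|
| ≥ 20 of 22 (plan) | 0.154 | 0.905 |
| ≥ 20 of 23 (cut-off left unchanged) | 0.297 | 0.974 |
| ≥ 21 of 23 | 0.133 | 0.895 |
| ≥ 22 of 24 | 0.115 | 0.884 |

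**The case against.** A reader might infer from section 5.2.14 that a proton plan with more than minor deviations is not delivered, so that poor plans are systematically replaced. The text does not support this. It classes constraint departures as planning deviations only and never says that a larger one stops a patient from starting; re-planning fits the wording equally well. Section 5.1.1 sets no plan-quality condition for the first fraction. Breaching a constraint is also not the same as failing the endpoint: the constraints are limits on many organs, while the endpoint is a 25% relative reduction in bowel DVH area against photons. A plan could breach a kidney limit and still meet the bowel criterion.

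A reader might also infer that the endpoint is already measured in every non-starter. The documents do not date the CT simulation relative to registration, the photon plans or the DVH extraction, and section 15.1.2 places the DVH publication after accrual. Backup use suggests that the photon plans exist near treatment start, but does not prove it. A patient who withdraws before planning has no DVH, and replacing her loses nothing.

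The size is also open to challenge. Step 3 assumes that no patient with a succeeding plan is lost; step 4 shows the figure falling when some are. Fourteen of the 22 were already treated, though the documents do not say whether any earlier registrants had been replaced.

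Finally, restricting to treated patients has a purpose: sections 1 and 14.1 relate DVH to toxicity, which requires treatment.

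All of this limits how likely and how large a bias would be. None of it gives a reason to drop a planned patient from the plan comparison. The toxicity correlation can keep its own treated set. Section 5.7 and the off-study form in 12.1.2 record reasons for leaving the study, but section 14 requires no reporting or analysis of non-starters.

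**Conclusion.** The point stands as a mismatch between the analysed group and the primary endpoint. Sections 14.2 and 14.5 apply a start-of-treatment rule to an endpoint that needs only completed plans, and no other section offsets it. This leaves room for selective loss; it is not evidence that selective loss occurs.

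The stated 15% error is correct as calculated and remains correct if replacement is unrelated to plan quality. The 20%, 30% and 55% figures (17%, 20% and 26% if only the last 8 places are affected) rest on three assumptions: a true rate of 80%, losses confined to failing-plan patients, and the chosen shares of 10%, 25% and 50%. They are a sensitivity range, not an estimate. The change is worth making because the rule is sensitive to a single exchanged patient and the remedy is cheap.

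**What to change.** Amend sections 14.2 and 14.5 as follows:

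- **Primary DVH set.** All registered patients with a completed proton plan and completed IMRT and 3DCRT plans, whether or not treatment starts, each scored on her actual DVH.
- **Replacement.** For this endpoint, replace only patients who were never fully planned.
- **Other endpoints.** Keep the start-of-treatment set for toxicity, quality of life, progression-free survival and the correlation of DVH with toxicity.
- **Cut-off.** Fix it in advance for denominators above 22, for example at least 21 of 23 (type I error 0.133, power 0.895) or at least 22 of 24 (0.115, 0.884).
- **Reporting.** Give the number of non-starters with reasons, separating those fully planned from those not.
- **Sensitivity analysis only.** Count as failures any planned patients whose proton plan was judged not deliverable. Doing this in the primary analysis would override a measured DVH and change the endpoint.

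The cost is a short amendment and retention of plans for planned non-starters. Power falls slightly, from 0.905 to 0.895 or 0.884 under the example cut-offs, and the success count may be slightly less favourable.

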14.3 Stratification Factors: N/A

14.4 Analysis of Secondary Endpoints:

CONFIDENTIAL

This document is confidential. Do not disclose or use except as authorized.

Secondary endpoints are QOL, progression-free survival and patterns of recurrence. QOL outcomes will be analyzed using mixed models for longitudinal data. Progression-free survival will be analyzed using standard methods for failure time data, primarily the Kaplan-Meier estimate. Progression-free survival is defined as the duration from the start of protocol treatment to the time of objective disease progression at any site or death in the absence of documented progression, while patients who have not progressed or died will be censored at the time of last follow-up. Differences between patient subgroups may be explored by the log-rank test, using exact methods as the event numbers will be modest. Patterns of recurrence will be reported descriptively.

14.5 Reporting and Exclusions;

All patients starting protocol therapy will be analyzed and reported for all study endpoints, whether or not treatment is completed.

14.5.1 Evaluation of toxicity.

All participants will be evaluable for toxicity from the time of their first treatment.

14.5.2 Evaluation of response. N/A. Patients with measurable disease are ineligible.

14.5.3 Evaluation of cancer control. At or before each scheduled follow-up surveillance visit patients will be categorized as clinically cancer-free, alive with cancer, dead from cancer, dead from complications of therapy, or dead from intercurrent illness, or cause of death unknown.

14.5.4 Pattern of cancer recurrence: In patients developing cancer recurrence, the pattern of recurrence will be recorded according to the criteria in 10.2 for local, regional and distant sites. As a patient may recur at multiple sites and at different times, the dates of recurrence will be recorded for each site. Progression-free survival will be based on the date of the earliest date of documented recurrence.

15. PUBLICATION PLAN

15.1.1 The intent of the investigators is to publish results in peer-reviewed journals.

15.1.2 A preliminary publication will compare DVH results from proton, IMRT, and 3DCRT plans after accrual has been completed.

CONFIDENTIAL

This document is confidential. Do not disclose or use except as authorized.

15.1.3 A second preliminary publication is anticipated when all surviving participants have been followed a minimum of 24 months following completion of protocol therapy, as the large majority of symptomatic late radiation complications will be manifest within this time window.

15.1.4 A final publication is anticipated when all patients have been followed a minimum of 5 years or until death.

15.1.5 Primary responsibility for publication will reside with the Principal Investigator (Study Chair) and may be delegated to the Division of Medical Physics for preliminary publication of comparative dosimetric results (endpoint 1.3.1).

CONFIDENTIAL

This document is confidential. Do not disclose or use except as authorized.

17. APPENDICES

CONFIDENTIAL

This document is confidential. Do not disclose or use except as authorized.

Appendix 1. Performance Status Criteria

ECOG Performance Status Scale		Karnofsky Performance Scale	
Grade	Description	Percent	Description
0	Normal activity. Fully active, able to carry on all pre-disease performance without restriction.	100	Normal, no complaints, no evidence of disease.
		90	Able to carry on normal activity; minor signs or symptoms of disease.
1	Symptoms, but ambulatory. Restricted in physically strenuous activity, but ambulatory and able to carry out work of a light or sedentary nature (e.g., light housework, office work).	80	Normal activity with effort; some signs or symptoms of disease.
		70	Cares for self, unable to carry on normal activity or to do active work.
2	In bed < 50% of the time. Ambulatory and capable of all self-care, but unable to carry out any work activities. Up and about more than 50% of waking hours.	60	Requires occasional assistance, but is able to care for most of his/her needs.
		50	Requires considerable assistance and frequent medical care.
3	In bed >50% of the time. Capable of only limited self-care, confined to bed or chair more than 50% of waking hours.	40	Disabled, requires special care and assistance.
		30	Severely disabled, hospitalization indicated. Death not imminent.
4	100% bedridden. Completely disabled. Cannot carry on any self-care. Totally confined to bed or chair.	20	Very sick, hospitalization indicated. Death not imminent.
		10	Moribund, fatal processes progressing rapidly.
5	Dead.	0	Dead.

CONFIDENTIAL

This document is confidential. Do not disclose or use except as authorized.

Appendix 2: FACT-En Version 4 Quality of Life Instrument for uterine cancer patients.

Below is a list of statements that other people with your illness have said are important.
Please circle or mark one number per line to indicate your response as it applies to the past 7 days.

PHYSICAL WELL-BEING		Not at all	A little bit	Some-what	Quite a bit	Very much
GP1	I have a lack of energy	0	1	2	3	4
GP2	I have nausea	0	1	2	3	4
GP3	Because of my physical condition, I have trouble meeting the needs of my family	0	1	2	3	4
GP4	I have pain	0	1	2	3	4
GP5	I am bothered by side effects of treatment	0	1	2	3	4
GP6	I feel ill	0	1	2	3	4
GP7	I am forced to spend time in bed	0	1	2	3	4
SOCIAL/FAMILY WELL-BEING		Not at all	A little bit	Some-what	Quite a bit	Very much
GS1	I feel close to my friends	0	1	2	3	4
GS2	I get emotional support from my family	0	1	2	3	4
GS3	I get support from my friends.....	0	1	2	3	4
GS4	My family has accepted my illness	0	1	2	3	4
GS5	I am satisfied with family communication about my illness.....	0	1	2	3	4
GS6	I feel close to my partner (or the person who is my main support)	0	1	2	3	4
Q1	Regardless of your current level of sexual activity, please answer the following question. If you prefer not to answer it, please mark this box  and go to the next section.					

GS7	I am satisfied with my sex life	0	1	2	3	4
-----	---------------------------------------	---	---	---	---	---

Please circle or mark one number per line to indicate your response as it applies to the past 7 days.

EMOTIONAL WELL-BEING

		Not at all	A little bit	Some- what	Quite a bit	Very much
GE1	I feel sad	0	1	2	3	4
GE2	I am satisfied with how I am coping with my illness	0	1	2	3	4
GE3	I am losing hope in the fight against my illness	0	1	2	3	4
GE4	I feel nervous	0	1	2	3	4
GE5	I worry about dying	0	1	2	3	4
GE6	I worry that my condition will get worse	0	1	2	3	4

FUNCTIONAL WELL-BEING

		Not at all	A little bit	Some- what	Quite a bit	Very much
GF1	I am able to work (include work at home)	0	1	2	3	4
GF2	My work (include work at home) is fulfilling	0	1	2	3	4
GF3	I am able to enjoy life	0	1	2	3	4
GF4	I have accepted my illness	0	1	2	3	4
GF5	I am sleeping well	0	1	2	3	4
GF6	I am enjoying the things I usually do for fun	0	1	2	3	4
GF7	I am content with the quality of my life right now	0	1	2	3	4

Please circle or mark one number per line to indicate your response as it applies to the past 7 days.

ADDITIONAL CONCERNS		Not at all	A little bit	Some-what	Quite a bit	Very much
01	I have swelling in my stomach area	0	1	2	3	4
03	I have cramps in my stomach area	0	1	2	3	4
Hep 8	I have discomfort or pain in my stomach area	0	1	2	3	4
ES6	I have vaginal bleeding or spotting	0	1	2	3	4
ES4	I have vaginal discharge	0	1	2	3	4
Hep 1	I am unhappy about a change in my appearance	0	1	2	3	4
ES1	I have hot flashes	0	1	2	3	4
ES2	I have cold sweats.....	0	1	2	3	4
ES3	I have night sweats	0	1	2	3	4
HI7	I feel fatigued.....	0	1	2	3	4
ES8	I have pain or discomfort with intercourse.....	0	1	2	3	4
En1	I have trouble digesting food.....	0	1	2	3	4
Bl1	I have been short of breath	0	1	2	3	4
Cx6	I am bothered by constipation	0	1	2	3	4
BL2	I urinate more frequently than usual.....	0	1	2	3	4
En2	I have discomfort or pain in my pelvic area	0	1	2	3	4

